### 6.4 STUDY INTERVENTION COMPLIANCE

The devices are electronic monitoring compliant – successful daily use is registered, also detects and records open circuits or failures. Primary and secondary outcomes are measured weekly and recorded by study team members electronically on secure databases.

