### 6.1.2 DOSING AND ADMINISTRATION

Each subject will have their tinnitus spectrum assessed with the Tinn Tester protocol (L. Roberts et al, 2008). This spectrum is digitized and programmed into the device as the signal to be delivered to the subject. The amplitude is limited to 95 dB SPL and is delivered together with an electrical stimulus delivered a short time after the auditory stimulus (as determined by the preclinical studies). This stimulus is presented by the device when the subject turns on the device. The device limits the time of presentation to 30-60 min per day.

This protocol is presented once a day for 30-60 minutes for 6 weeks. After that there is a washout period of 6 weeks in which no device is used. Subjects are tested once a week to assess the primary and secondary outcomes and when baseline is achieved. The second arm of the study begins for another 6 weeks. A second washout of 6 weeks occurs, end of study visit, and 12 weeks of follow up, after which the subject participation is ended. Completion of Arm 1 and Arm 2 do not necessarily have to be consecutive, and we will allow for 12 weeks in between in order to provide more flexibility for subjects. The dose will not change over the course of the study. Maximum duration of enrollment is 36 weeks.

The subjects will be trained on how to use the devices and place the earphones and electrode pads. Once they have been effectively trained, subjects will take the devices home to use for the 30-60 min/day periods. Once a week the primary and secondary outcomes will be tested along with any review or questions that the subjects need to be answered. Subjects are asked to use the device at the same time every day but If subjects miss a treatment they are instructed to use it at another time rather than miss that treatment.

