### 7.3 LOST TO FOLLOW-UP

A participant will become ineligible to continue in the study if he/she misses more than one visit for each of the following 6-week time periods: Arm 1 treatment, Arm 1 washout, Arm 2 treatment, Arm 2 washout. It is not considered a protocol deviation if a subject misses only one visit in any 6-week time period. A participant will be considered lost to follow-up if he or she fails to return for 2 consecutive scheduled visits and is unable to be contacted by the study site staff.

The following actions must be taken if a participant fails to return to the clinic for a required study visit:

- The site will attempt to contact the participant and reschedule the missed visit within 1 week and counsel the participant on the importance of maintaining the assigned visit schedule and ascertain if the participant wishes to and/or should continue in the study.
- Before a participant is deemed lost to follow-up, the investigator or designee will make every effort to regain contact with the participant (where possible, 3 telephone calls, emails or portal messages).
- Should the participant continue to be unreachable, he or she will be considered to have withdrawn from the study with a primary reason of lost to follow-up. If participant refuses to return device, the Office of General Council and/or the UM Police department will be notified of device theft, pursuant to Mich. Comp. § 750.356(3), § 750.356a(1), "Felony Theft in Michigan".

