## 8 STUDY ASSESSMENTS AND PROCEDURES

### 8.1 EFFICACY ASSESSMENTS

#### Study Procedures:

**General overview:** All subjects will complete consenting and then a candidacy evaluation to determine if they meet study criteria. Once they meet criteria, they will be scheduled for a baseline re-assessment. Following the baseline assessment, they will be randomly assigned to a study arm (treatment or sham) and then training on how to use the device before taking it home. They will take home the device on the same day they complete the baseline assessment. Follow up assessments will take place weekly, and assessments completed at the weekly session are noted below. Additionally, some measures will only be completed at the beginning or end of the active treatment or sham conditions and following washout of active or sham treatment.

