### 9.4.2 ANALYSIS OF THE SECONDARY ENDPOINT(S)

The following analytical framework will be applied to 2ndary measures (see section 3.2 for more details). Analyses are not dependent on primary-measures. All measures are ordinal, repeated measures. Data will be analyzed using repeated-measures ANOVA, and shown as mean+/-SEM. Normality will be assessed using Kolmogorov-Smirnoff tests, and non-parametric tests used for non-normally distributed data. To assess how the secondary measures might co vary with the primary measures, we will use principal component analysis or linear fixed effects models.

Non-compliant and missing data points will be excluded from analysis.

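### MML and THS have two measurement schedules, and the secondary analysis names no time points while excluding missing readings from a repeated-measures ANOVA

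*Combined protocol and SAP*

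**What the plan says.** **Weekly.** Section 6.4: "Primary and secondary outcomes are measured weekly and recorded by study team members electronically on secure databases". Section 6.1.2 says of washout, "Subjects are tested once a week to assess the primary and secondary outcomes and when baseline is achieved", and of the home-use period, "Once a week the primary and secondary outcomes will be tested along with any review or questions". None of these sentences makes an exception, and MML and THS are named secondary endpoints in the synopsis and in 9.1.

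**At period boundaries.** The Schedule of Activities (1.3) marks THS and MML (printed there as MMI) in five alternate columns. By position these are Baseline 1 and the ends of weeks 6, 12, 18 and 24. TFI, THI and TinnTester are marked in the weekly columns too. The overview in 8.1 says that "some measures will only be completed at the beginning or end of the active treatment or sham conditions and following washout". Items 6 and 9 of the specific procedures in 8.1 place MML and THS at the baseline evaluation and then refer to the Schedule.

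**Analysis.** Section 9.4.2: "Data will be analyzed using repeated-measures ANOVA, and shown as mean+/-SEM" and "Non-compliant and missing data points will be excluded from analysis". It does not say which readings enter. Section 9.3 prescribes LOCF for missing data and losses to follow-up, and does not limit it to the primary endpoints.

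**Attendance.** Section 7.3: "It is not considered a protocol deviation if a subject misses only one visit in any 6-week time period". A subject who misses more than one visit in a period becomes ineligible to continue. The site tries to reschedule a missed visit within 1 week.

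**The concern.** Staff cannot follow both schedules. A weekly visit without MML and THS complies with the Schedule but departs from 6.1.2 and 6.4. Depending on which text is followed, a subject has 4 or about 24 post-baseline readings of each measure.

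The analysis section does not settle the matter. A classical repeated-measures ANOVA needs a value at every level of the repeated factor, so excluding one missing reading normally removes the whole subject. A subject who stays within 7.3 can miss up to four visits, one in each of the four 6-week periods. Such a subject has followed the protocol yet may drop out of the secondary analysis, and those who remain are selected for attendance. How many are lost depends on which readings enter the model and which missing-data rule governs. The plan leaves the first open and answers the second in two ways.

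**Working it through.** The plan has no figure of its own to reproduce here. The sample size in 9.2 (2 × 17 = 34, planned minimum 50) is derived for loudness and TFI. No missed-visit rate, and no power for MML or THS, is given.

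**1. Number of readings.** Four periods of six weekly visits give 4 × 6 = 24 post-baseline occasions. (The day row of the Schedule gives 25, because weekly days run to 84 and the second baseline falls on day 91.) The boundary version gives 4. The Schedule's column alignment is worth checking on the printed page, but the alternating pattern for THS and MML is plainly different from the unbroken rows for TFI, THI and TinnTester, and it fits the baseline start stated in 8.1.

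**2. Share of complete subjects.** Assumptions: each visit is missed and not recovered with probability *p*, independently; baseline is complete; one missing reading removes the subject; only subjects retained under 7.3 are counted (at most one miss in each period).

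For one 6-visit period:
- no miss: P0 = (1 − p)^6
- exactly one miss: P1 = 6p(1 − p)^5

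Among retained subjects:
- complete on all 24 readings: [P0/(P0 + P1)]^4
- complete on the 4 boundary readings: [1 − (P1/6)/(P0 + P1)]^4, because a single miss falls on the boundary visit one time in six

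At p = 0.05, P0 = 0.735, P1 = 0.232 and their sum is 0.967.
- Weekly: (0.735/0.967)^4 = 0.760^4 = 0.334
- Boundary: (1 − 0.0387/0.967)^4 = 0.960^4 = 0.849

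| Assumed p | Complete, 24 weekly readings | Complete, 4 boundary readings |
|---|---|---|
| 1% | 79% | 96% |
| 2% | 63% | 93% |
| 3% | 51% | 90% |
| 5% | 33% | 85% |
| 10% | 13% | 76% |

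**3. When the weekly version loses a majority.** Setting the weekly share to one half gives P0/(P0 + P1) = 0.5^(1/4) = 0.841. More than about 16% of retained subjects must then use their allowed miss in each period, which corresponds to p above about 3.1%. If misses cluster within subjects (beta-binomial, intraclass correlation 0.02 to 0.10, not conditioned on 7.3), the threshold rises to about 3.5% to 5.7%.

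**4. What removes the loss.** If the ANOVA uses only the four times in the endpoint table of section 3, the right-hand column applies: about 15% lost at p = 5%. If LOCF under 9.3 governs, an intermittent miss removes nobody, but carried-forward values then stand in for readings that were not taken.

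**The case against.** The case on the other side is substantial.

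- **Section 8.1 already points to the Schedule** for MML and THS, so 6.1.2 and 6.4 can be read as loose summaries. They are also partly true: bandwidth is a secondary outcome and is collected weekly through TinnTester. This stands. Taken alone, the schedule mismatch is close to clerical.
- **A reader might infer that the plan will lose most subjects from the secondary analysis.** The documents do not support that. It needs all 24 weekly readings in the model, whole-subject deletion (9.4.2 speaks of data points, not subjects), no LOCF, and an unrecovered missed-visit rate above about 3%. No such rate is given, and the rescheduling attempt in 7.3 would lower it.
- **A reader might take the endpoint table as proof that MML and THS are measured only at boundaries.** It lists the same four times for loudness, TFI and THI, which are measured weekly. It shows which times are endpoints, not how often a measure is taken. The contradiction therefore rests on the Schedule and on 8.1.
- **A reader might convert the loss of subjects into a loss of power.** The plan states no effect size or power for any secondary endpoint, so such a figure would be invented.

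These objections do not remove the analysis problem. Section 9.4.2 is the specific rule for secondary endpoints and calls for exclusion, while the general rule in 9.3 calls for carrying forward. Even with four time points, the ANOVA with exclusion discards subjects over a single missing reading.

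**Conclusion.** The point holds in a limited form. Sections 6.1.2 and 6.4 contradict the Schedule for MML and THS; 8.1 favours the Schedule, so that repair is wording. The more consequential weakness is 9.4.2: it names no time points, conflicts with 9.3 on missing data, and uses a method that normally drops a subject for one missing reading although 7.3 tolerates such gaps.

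At an assumed 5% of unrecovered misses, independent across visits, the cost is about 15% of retained subjects on the four boundary readings. It would be about 67% if all 24 weekly readings entered. The second figure is conditional on a reading of the plan that the documents leave open but do not state. Bandwidth has no schedule contradiction and is not part of this point.

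**What to change.** 1. In 6.1.2 and 6.4, replace the blanket weekly statements so that they agree with the Schedule: loudness, bandwidth, TFI and THI weekly; MML and THS at Baseline 1 and the ends of weeks 6, 12, 18 and 24.
2. In 9.4.2, name the four endpoint-table times (end of each arm and end of each washout) as the analysis points for MML and THS.
3. In 9.4.2, replace the repeated-measures ANOVA with exclusion by a mixed model with a random subject intercept, as 9.4.1 already uses for the primary endpoints, fitted to all available readings. A subject with one missing reading then stays in. The model relies on readings being missing at random, which should be stated.
4. State in 9.3 and 9.4.2 that this replaces LOCF for the secondary endpoints, so that one missing-data rule applies.

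Bandwidth need not be cut back to the boundary readings. The cost is minor analysis rewording, with no added visits or tests. Any weekly MML or THS readings already taken become descriptive. The change should be made before unblinding, so that the choice between 4 and 24 readings is not made with the results in view.

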### 6.5 CONCOMITANT THERAPY

NA

#### 6.5.1 RESCUE MEDICINE

NA

## 7 STUDY INTERVENTION DISCONTINUATION AND PARTICIPANT DISCONTINUATION/WITHDRAWAL

### 7.1 DISCONTINUATION OF STUDY INTERVENTION

This study uses a non-invasive device. We will use strictly calibrated instruments to ensure that both acoustic and electrical stimulation are being delivered at safe levels for each subject. However, specific stopping rules will be identified for each subject to ensure patient safety. For each subject, data for the TFI, THI, and TinnTester will be examined on a weekly basis (following weekly testing for each subject) for tinnitus assessments. Additionally, audiometric criteria will be assessed at least every 6 weeks (please see schedule of events) to monitor hearing status. Audiometric criteria will be evaluated during the interim if a subject reports concern for a change in hearing ability. This metric will be monitored by the ISM. If tinnitus is found to statistically, significantly increase according to aggregated mean baseline, then the subject will not continue in the study regardless of which arm (active or sham) in which the subject is enrolled. Furthermore, if the subject subjectively reports increase in tinnitus or worsening of hearing, without a significant change in any of the subjective or objective measures, and he/she wishes to discontinue participation in the study then he/she will withdraw from the study.

A subject's participation in the study will be discontinued following **both** 1) an increase of 16 or more points in TFI, **and** 2) an average increase of 12 dB in TinnTester compared to baseline, for two consecutive weekly measures. Both measures are our primary outcome measures. Using both criteria for determining discontinuation is critical as the tinntester measures tinnitus loudness, which reflects the circuitry changes identified in our preclinical studies. TFI is also important for the human study as it gauges the subject's subjective response to their tinnitus. However, TFI can also reflect outside life stressors unrelated to the treatment and could result in a subject's discontinuation for reasons unrelated to the treatment.

### 7.2 PARTICIPANT DISCONTINUATION/WITHDRAWAL FROM THE STUDY

- Pregnancy
- Significant study intervention non-compliance
- If any clinical adverse event (AE), laboratory abnormality, or other medical condition or situation occurs such that continued participation in the study would not be in the best interest of the participant
- If the participant meets an exclusion criterion (either newly developed or not previously recognized) that precludes further study participation
- Participant becomes unable to participate in the study on a weekly basis.

The reason for participant discontinuation or withdrawal from the study will be recorded on the Case Report Form (CRF). Subjects who sign the informed consent form and are randomized but do not receive the study intervention may be replaced. Subjects who sign the informed consent form, and are randomized and receive the study intervention, and subsequently withdraw, or are withdrawn or discontinued from the study, will be replaced.

### 7.3 LOST TO FOLLOW-UP

A participant will become ineligible to continue in the study if he/she misses more than one visit for each of the following 6-week time periods: Arm 1 treatment, Arm 1 washout, Arm 2 treatment, Arm 2 washout. It is not considered a protocol deviation if a subject misses only one visit in any 6-week time period. A participant will be considered lost to follow-up if he or she fails to return for 2 consecutive scheduled visits and is unable to be contacted by the study site staff.

The following actions must be taken if a participant fails to return to the clinic for a required study visit:

- The site will attempt to contact the participant and reschedule the missed visit within 1 week and counsel the participant on the importance of maintaining the assigned visit schedule and ascertain if the participant wishes to and/or should continue in the study.
- Before a participant is deemed lost to follow-up, the investigator or designee will make every effort to regain contact with the participant (where possible, 3 telephone calls, emails or portal messages).
- Should the participant continue to be unreachable, he or she will be considered to have withdrawn from the study with a primary reason of lost to follow-up. If participant refuses to return device, the Office of General Council and/or the UM Police department will be notified of device theft, pursuant to Mich. Comp. § 750.356(3), § 750.356a(1), "Felony Theft in Michigan".

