## 9.2 SAMPLE SIZE DETERMINATION

To compute statistical power, we utilized a linear model of our prior trial data, where change from baseline in both TFI and loudness is a linear function of the time in study, with a constant term reflecting enrollment in study. Time in study was extended out to six weeks. Data sample independence was achieved by normalizing each subject by their own baseline. With these parameters, alpha = 0.05 and beta = 0.8, we simulated new data sets with samples ranging from 5 to 50. Model slopes were tested for significant differences using analysis of covariance. Each new model was simulated 50 times, and the total number of significant models counted. The first sample size where the computed power was greater than 0.8 was determined. 14 subjects are required per arm to achieve a power of 0.8 for the loudness test, and 17 subjects are required per arm for the TFI. Thus, this study design requires a total subject count of 34. We propose a minimum sample size of 50 to account for subject variability and compliance.

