## 9.3 POPULATIONS FOR ANALYSES

All subject's data will be analyzed in one cohort. We will perform both per-protocol and intention-to-treat analyses. While intention-to-treat analysis is ideal, our protocol may require subjects to adhere to a strict schedule in order to fully realize the benefit of the treatment. Our pilot study had excellent compliance rates, but a longer and larger study provides more opportunity for non-compliant subjects. Should sensitivity analysis between the intention-to-treat and per-protocol analyses attain significance, differences between compliant and non-compliant subjects will be further explored in an effort more fully understand who best can benefit from the bimodal protocol. Missing data and losses to follow-up will be managed using

a last observation carried forward approach. Sensitivity analysis to outliers will also be performed. If results differ significantly between with and without outliers, outliers will be further investigated to determine what factors impact the likelihood of a subject responding or being resistant to the treatment protocol.

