## 9.4 STATISTICAL ANALYSES

Data will be analyzed as means with standard deviations. All hypothesis-testing derived analyses will utilize an alpha of 0.05, beta of 0.8, and utilize two-tailed tests.

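### Sections 7.2 and 7.3 end outcome collection for subjects who miss visits or do not comply, so for them the intention-to-treat analysis in 9.3 rests on imputation or model assumptions; 9.4.2 contradicts 9.3 for the secondary endpoints

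*Combined protocol and SAP*

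**What the plan says.** Section numbers follow the body of the protocol; the table of contents numbers the analysis subsections one higher.

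- **Removal for missed visits (7.3).** "A participant will become ineligible to continue in the study if he/she misses more than one visit" in the listed six-week periods: Arm 1 treatment, Arm 1 washout, Arm 2 treatment, Arm 2 washout. The site is to try to reschedule a missed visit within a week.
- **Removal for other reasons (7.2).** The reasons for leaving the study include "Significant study intervention non-compliance" and becoming unable to take part weekly.
- **Replacement (7.2).** Subjects who were randomised and received the intervention "and subsequently withdraw, or are withdrawn or discontinued from the study, will be replaced".
- **After removal.** No section provides for assessing a subject who has been removed.
- **Analysis sets (9.3).** "We will perform both per-protocol and intention-to-treat analyses". Neither set is defined and neither is named as primary. Missing data and losses to follow-up are handled by last observation carried forward.
- **Primary endpoints (9.4.1).** A mixed model with a random intercept, described as able to cope with missing data. Nothing is excluded for non-compliance.
- **Secondary endpoints (9.4.2).** Repeated-measures ANOVA. "Non-compliant and missing data points will be excluded from analysis".
- **Timing (1.3 and 3).** The endpoints are read at the end of each arm and each washout. TFI, THI and TinnTester are also scheduled weekly.

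**The concern.** An intention-to-treat analysis needs outcomes on the subjects who attend poorly or use the device poorly. Those are the subjects for whom 7.2 and 7.3 stop collecting outcomes, even when the next end-of-arm visit could still be attended.

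Who stays then depends on events after randomisation. Section 6.3 itself accepts that blinding may be imperfect because of the electrical stimulation, so the reasons for leaving could differ between active and sham. In a crossover, a subject removed during Arm 1 or the first washout has no observed second-arm outcome and so no observed active-sham contrast. Replacing that subject restores the count but not the missing outcome.

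Section 9.3 expects some non-compliance in this longer, larger trial and plans to learn from comparing intention-to-treat with per-protocol results. The less that is observed on non-compliers, the less that comparison can show.

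**Working it through.** **1. The plan's own figures (9.2).** For loudness the plan says that "14 subjects are required per arm to achieve a power of 0.8 for the loudness test". The second calculation, on the questionnaire score, concludes that "17 subjects are required per arm for the TFI". The larger figure gives 2 × 17 = 34, the stated total. The 14 and 17 come from a simulation whose slopes and variances are not given, so they cannot be reproduced. The stated minimum is 50, partly to allow for compliance: 1 − 34/50 = 32%. If 32% of 50 were lost, 50 × 0.68 = 34 would remain. The minimum of 50 therefore already carries an allowance without replacement.

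**2. How many the missed-visit rule could remove.** Inputs: six weekly visits per period and four periods (1.3 and 7.3). Assumptions: each visit is missed independently with probability p, no missed visit is made up, and two or more misses in *any* one period lead to removal.

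- One period: P = 1 − (1−p)^6 − 6p(1−p)^5
- Before Arm 2 (two periods): 1 − (1−P)^2
- All four periods: 1 − (1−P)^4

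| p | P | Before Arm 2 | All four periods |
|---|---|---|---|
| 3% | 0.0125 | 2.5% | 4.9% |
| 5% | 0.0328 | 6.4–6.5% | 12.5% |
| 10% | 0.1143 | 21.6% | 38.5% |

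The middle column counts subjects with no observed second-arm outcome. The last column also includes subjects removed in the second washout, who have already finished both arms.

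The *for each of* wording in 7.3 can also be read as requiring two misses in all four periods. Then the probability is P^4, or 0.0002 at p = 10%. On that reading the rule could not act before the last period. The next sentence of 7.3, on missing a single visit in any six-week period, favours the per-period reading.

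**3. The missing-data rules side by side.**

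| Section | Scope | Rule |
|---|---|---|
| 9.3 | All analyses, no restriction stated | Last observation carried forward |
| 9.4.1 | Primary | Mixed model said to account for missing data |
| 9.4.2 | Secondary | Missing and non-compliant points excluded |

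These are three different treatments. The third also conflicts with 9.3, because dropping non-compliant points is a per-protocol restriction and no intention-to-treat version of the secondary analyses is given.

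**4. What carrying forward does across periods.** Section 9.3 does not confine it to a period. Take an active-first subject removed during Arm 1 with last value y. The end-of-active value is y and the end-of-sham value is also y, so the active-sham difference is y − y = 0 by construction. For a subject removed in the first washout, a washout value stands in for the second-arm outcome. In both cases one condition is filled with data from another.

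**5. What retaining everyone could cost in power (illustrative).** Section 9.4 says "All hypothesis-testing derived analyses will utilize an alpha of 0.05, beta of 0.8, and utilize two-tailed tests"; the 0.8 is read as power. Back-solving 17 per arm with a parallel-group normal approximation gives d = (1.960 + 0.842) × √(2/17) = 0.96 SD. Suppose a fraction r is removed, contributes zero effect and is kept without replacement. With 50 randomised, power = Φ(0.961(1−r)√12.5 − 1.96):

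| r | 0% | 10% | 20% | 32% |
|---|---|---|---|---|
| Power | 0.92 | 0.86 | 0.78 | 0.64 |

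With 100 randomised, the ceiling in 5.5, the figures are 0.998, 0.99, 0.97 and 0.90. Zero effect in every removed subject is an assumption, and the crossover model would behave differently.

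**The case against.** The strongest reply is that the plan already deals with dropouts. Weekly TFI, THI and TinnTester data exist up to removal, the mixed model can use them, and 9.3 names an imputation rule. This stands. A reader might infer from 7.2 and 7.3 that the intention-to-treat analysis cannot be carried out and that the trial becomes a trial of completers. The documents do not support that. No section takes removed or replaced subjects out of the intention-to-treat set, and nothing says that the two analysis sets would coincide.

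Nor does the exclusion in 9.4.2 defeat the primary analysis: it sits under the secondary endpoints, and 9.4.1 has no counterpart.

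On size, rescheduling within a week and the three-day visit window would lower the figures above, and 9.3 reports excellent compliance in the pilot. The ceiling of 100 against a minimum of 50 is not a forecast that half will be replaced; the summary of changes ties the increase to subjects left incomplete by the pandemic shutdown. Different loss between active and sham is possible but not shown, and no device is used in two of the four periods.

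Weekly visits also have a safety purpose in 8.2, and the individual stopping rule uses two consecutive weekly measures. That may be a reason to stop device use. It is not a reason to stop collecting outcomes.

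**Conclusion.** The concern holds in a limited form. Sections 7.2 and 7.3 end study participation, not only device use, for missed visits or non-compliance; replacement of treated subjects is mandatory; and nothing is collected afterwards. The intention-to-treat analysis remains possible, but for removed subjects it would depend on carried-forward values or on the mixed model being right about data never observed. Carrying a value into Arm 2 is the weakest part. The conflict between 9.3 and 9.4.2 is separate and concerns the secondary endpoints only.

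The size is not known from the documents. Under independence, the any-period reading and no rescheduling, roughly 2.5% to 22% would be removed before Arm 2 and 5% to 38% overall, for miss rates of 3% to 10% per visit. Removal for non-compliance would add to this, and *significant* is not defined. No figure in the plan is shown to be wrong. This should be fixed, because outcomes not collected cannot be recovered later, but it does not invalidate the plan.

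**What to change.** 1. **7.2 and 7.3.** Leave the rules on device use and safety stopping to the sponsor. State that subjects removed for missed visits or non-compliance are, unless consent is withdrawn, still invited to the already scheduled end-of-arm and end-of-washout assessments. Clarify whether the missed-visit limit applies to any one period or to all of them.
2. **9.3.** Define the intention-to-treat set as all randomised subjects by assigned sequence. Say that replaced subjects stay in it and that replacements are additional.
3. **9.4.2.** Analyse all observed data by randomised sequence, and keep the compliance restriction for the per-protocol set only.
4. **9.3, 9.4.1 and 9.4.2.** Use one missing-data approach: the mixed model on observed data, with no values carried across periods.

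The cost is amendment wording and a few extra attended visits. The estimated effect may be smaller because non-compliers are included, and the loss of power could matter if many are removed; that is the effect an intention-to-treat analysis is meant to estimate. One limit remains: a subject who does not receive the second-arm device still has no active-sham contrast under both treatments, but the outcome under the assigned sequence would be observed instead of imputed.
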